#### 6.0 Risks to Participants

For this study, in Aim 1, we will be utilizing existing data resources under a currently approved IRB protocol #17-9031. Only geocoded (census tract level), de-identified data will be used for analysis. We will provide additional protections for our deocoded study populations as follows. If we are provided patient addresses, we will employ a "false coordinate system" to decouple household addresses from individual personal data attributes. That is, we will map the data in such a way that the true geographic location is not stored in the GIS software. For instance, the actual position of an address might be described by the coordinates: -125.652, 24.229 (see the illustration below). The statistical tools within GIS enable us to very simply alter the true coordinate values by adding or subtracting a fixed value to all the X and Y geographic coordinates in the dataset. We intend to employ a "minimum-maximum false coordinate range" of values 1-8 — to ensure that the confidentiality of the study participants' household addresses are, not in any way, compromised. Further, for areas or census tracts with a minimal number of patients (i.e. <6 patients), we will employ geographic aggregation and geomasking techniques to further protect confidentiality[14, 16] Given we are working with geocoded, de-identified registry data for analysis and employing patient protections during the collection, storage, and analysis of data, this study represents minimal risk to participants.

There is no physical risk to participants. There is a however a small risk that participant(s) may feel uncomfortable answering some questions on the survey. Participants will be informed of their options to not answer any question they are uncomfortable responding to.

The study team will make every effort to keep the information provided in the study confidential.

- All information gathered during this study will be kept in locked cabinets or in electronic databases that are password-protected.
- The study team will delete your name and other information that might identify participants, whenever possible.

Additional Protections Against Risk. Fox Chase Cancer Center (FCCC) participates in the Collaborative Institutional Training Initiative (CITI) on-line education program. In order to participate in the conduct of research, all research personnel involved with human subjects research must complete the tutorials designated as applicable to their research role. Test dates and results are on file with the FCCC Institutional Review Board Office and Human Subjects Protection Office. Investigators/staff participating in this project will complete CITI training (and have evidence of current certification on-file). In addition, all research personnel will be in compliance with the Health Insurance Portability and Accountability Act (HIPAA) and other federal/state regulations.

Every effort will be made to protect participants against risk. All participants, will be told that they do not have to answer any questions that they do not want to answer and that they have the right to withdraw from the project at any time. Data will be collected and maintained in a manner that will not jeopardize the integrity of the project, but more importantly the privacy and confidentiality of the participants.

Study processes regarding to data entry, data management are outlined in Section 5.0.

Only persons directly involved with the project will have access to data identifying individuals. No names will be stored on computer files for data analysis, and no individuals will be identified in the results of this project. Access to computer-stored information will require simultaneous

knowledge of the data format, computer language, file name, and password. We anticipate no significant risks

#### 7.0 Potential Benefits to Participants

There may or may not be direct benefits to the participants of this project. The information learned from this project may benefit underserved populations in our Primary Service Area and will contribute to our efforts to better target prevention programs for liver disease and liver cancer.

FCCC is committed to focusing its clinical and research enterprise on vulnerable populations. The proposed local data collection will provide new, potentially "actionable" information about risk behaviors, cancer knowledge/attitudes, cancer information access/usage, and cancer screening knowledge/access/usage across the various populations served by FCCC. Data/insights gathered from the large, at risk, minority population will be of crucial importance. The proposed project will also provide the Center with a deeper understanding of knowledge/attitudes about screening testing among the populations FCCC serves, which will in turn allow us to more effectively engage them in community-based, hypothesis-driven, research initiatives moving forward.

The specific areas of health benefit to the populations served by FCCC will not be appreciated until the data are analyzed and strategies to align the Center's research initiatives with the cancer burden in the catchment area Primary Service Area, optimize cancer prevention and control efforts, and increase inclusion of minorities in clinical research/trials and biobanking research have been implemented. Nonetheless, because the proposed study poses minimal risks to participants, the potential health benefits to the populations served will likely greatly outweigh any potential risks to participants.

#### 8.0 Provisions to Maintain the Confidentiality of Data

Research study staff and the FCCC Population Studies Facility will maintain project data in confidence according to the rules and regulations of FCCC, the ICR, the FCCC/TU IRB, and HIPAA requirements. All information which could potentially identify participants will be maintained on a separate secured database. All paper files with identifiable information will be stored under lock and key at all times. All computer systems will be password-protected against intrusion; all network-based inter-site communications of confidential information will be encrypted.

An on-going computer virus protection program is available and utilized, maintained, and audited on all computers and pathways into the system, including good practice policies, screening of data files, executable software, diskettes, text macros, downloads, and other concerns as they arise. The redundant backups described above allow for quick restoration of data in the unlikely event that a security breach (or the more likely event of a hardware failure) occurs. Patient addresses will be removed from the dataset once geocoding is complete, and only geocoded, de-identified data will be used for analysis. Identifiers will be stored separately from study data, and all identifiers and linkages will be destroyed 7 years after the completion of this study.

#### 9.0 Costs to Participants

There is not cost associated with this project. Neither community partners nor participants will incur any costs.

## 10.0 Consent Process

Informed consent will be obtained from all participants prior to study participation. The informed consent form has been written at a 6.9 grade level and has been reviewed by the health communications director at Fox Chase. The health educator will read aloud the consent to participants and participants will be given time to ask questions before they sign consent forms (or indicate verbal consent). Participants with email access will be offered the opportunity to be sent the verbal consent form via email so that they may read the form along with the recruiter during the consent process. Once the individual fully understands each element of the consent, including the purpose, requirements, risks, confidentiality, right to withdraw, and contact person, the individual will be asked to provide informed consent. Eligible participants will be given a copy of the consent form). Participants who consent in person will be given a copy of the consent form at the time of consent, and those who consent verbally over the telephone will be sent a copy of the consent form via U.S. Mail. Consents will be translated into Spanish and submitted as a modification in the event we plan to enroll Spanish-speaking participants.

The informed consent process for both in-person and telephone verbal consent will be documented in detail, and research staff will date and sign the informed consent document. The original paper copy of the signed/countersigned document will stored in the participant's file, as well as uploaded into the study REDCap database.

# 11.0 Off-Study Criteria

Not applicable

**12.0 Drugs and Devices** Not applicable

13.0 Multi-Site Research Study

Not applicable

# 14.0 Statistical Analysis

**14.1 Spatial Analysis**. The dataset for the geospatial analysis is de-identified, and geospatially aggregated to protect patient confidentiality[14]. Spatial analyses will be conducted by Fox Chase Cancer Center/Temple University using SatScan spatial scan statistics that empirically identify neighborhood clusters at the census tract level wither higher than expected rates of liver cancer [17], similar to existing protocol #17-9031. Mapping will be completed using ArcGIS 10.2 software (www.esri.com).

**14.2 Participant Self-Report Data.** Demographics will be summarized using descriptive statistics. Statistical analysis for efficacy of the education sessions will include changes in knowledge, changes in self-efficacy, and intention. Mean differences will be calculated in self-report outcome measures at pre- and post-survey, along with standard deviations and the effect size (mean difference/SD of the differences). We will compare the pre-post differences using t-tests or Wilcoxon tests, as appropriate.

**14.3 Power**. The sample size calculations are based on the primary outcomes for the pre-post evaluation of the education intervention. We assume a standard effect size of 0.3-0.4 on the primary outcomes (0.3-0.4 times the standard deviation of the pre-post changes for the

measures). We therefore aim to accrue up to 100 patients (but no less than 50) to have 80% power to detect a standard effect of 0.3-0.4, with 5% two-sided type-I error.

**14.4 Limitations**. Modifiable area unit problem (MAUP) will be evaluated and appropriate scale, aggregation, and cluster size will be considered for geospatial analysis.

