The PowerPoint liver module is written at a 7.3 grade level and has been vetted for accuracy by clinician [name] at Fox Chase Cancer Center. Behavioral Scientists, [name]., [name]. and OCO Sr. Director [name] have developed the pre/post tests. The final versions has been reviewed by the director of health communications, [name] for plain language review. Once approved by IRB, OCO will proceed with translation of the documents into Spanish, using the TUHS approved vendor(s).

Because in-person education sessions cannot be held during the COVID-19 pandemic, the educational slides will be converted to a set of handouts that will be sent to the participant (along with the educational brochure). The educational intervention materials will be sent via US mail to participants who do not have reliable internet access, and those who prefer to view the materials online will be offered the choice of having them emailed or texted, or viewing them on Zoom. The health educator will call the participant to review the educational materials over the telephone (or Zoom). By default, the intervention will be conducted over the telephone and only participants who indicate that they are comfortable utilizing a web platform will be offered the intervention over Zoom (or a similar program). Zoom instructions will be given over the telephone at the time of the intervention to those who opt to receive the intervention online. For analysis purposes, intervention delivery method (pre-COVID in-person/telephone/online) will be tracked, as well as the timing of the intervention relative to consent and baseline (immediate administration, i.e., after materials are mailed to the participant after consent and baseline).

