#### **B. Study Survey**

Once eligibility has been confirmed, informed consent has been obtained, participants will fill out a sign-in sheet that includes their street address. If the participant agrees to be contacted about this or future research after their participation, they will also be asked to write their telephone number on this form. Because the sign-in sheet contains identifiable information, it will be kept separate from survey data and will be linked by a study ID assigned to the participant after consent. The street address data will be geocoded for neighborhood analysis. Telephone numbers will be stored in a secure database. Once geocodes are created from the street addresses, hard copies of the sign-in sheets will be destroyed. After the sign-in sheet is collected, the study survey will be administered. Once approved, the English survey will be translated into Spanish language. Once translated, a modification will be submitted.

The study "pre" survey will be administered post informed consent process and prior to the educational intervention by OCO health educators (field staff). Upon completion of the educational module, a posttest survey will be administered. All survey data will be entered in the RedCap database.

Both the pre- and post-survey will contain measures of knowledge about liver risks and prevention, self-efficacy about talking to medical professionals about neighborhood risk, as well as demographic items (e.g. gender, race/ethnicity). The post survey will include similar knowledge questions as well as additional questions specifically related to neighborhood health, including a program evaluation, outcome expectancies about learning about neighborhood health (i.e., the extent to which leaning about neighborhood health will be beneficial), and intentions to talk with clinicians about liver cancer, neighborhood health and liver cancer screening. **Primary outcomes** include pre-post changes in knowledge about liver cancer, interest in learning about neighborhood health, outcome expectancies for learning about neighborhood health, and participant intentions for talking to their doctors about liver cancer risk.

During COVID-19 closures, the survey will be administered over the telephone. Mailing and street address will be collected during recruitment, so that informed consent copies and intervention materials can be mailed to the participant.

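### Participants taught remotely are likely to have the mailed slides at hand for the knowledge post-test but not for the pre-test, which could overstate a primary outcome

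*Combined protocol and SAP*

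**What the plan says.** Section 4.4B lists the primary outcomes, which "include pre-post changes in knowledge about liver cancer, interest in learning about neighborhood health", outcome expectancies and intentions. Both surveys contain knowledge questions. The order for the second survey is "Upon completion of the educational module, a posttest survey will be administered".

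Section 4.3B changes delivery during the pandemic: "the educational slides will be converted to a set of handouts that will be sent to the participant (along with the educational brochure"). People without reliable internet get the materials by post, while "those who prefer to view the materials online will be offered the choice of having them emailed or texted, or viewing them on Zoom". The educator then reviews them with the participant, by telephone unless the participant is comfortable with a web platform. Section 4.4B adds: "During COVID-19 closures, the survey will be administered over the telephone".

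The one statement about when materials arrive relative to the pre-test is in 4.3B. It is an explanatory parenthesis about the timing to be tracked: "after materials are mailed to the participant after consent and baseline".

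Section 14.2 gives the analysis: "Mean differences will be calculated in self-report outcome measures at pre- and post-survey, along with standard deviations and the effect size", followed by t-tests or Wilcoxon tests. It names no grouping, so I read it as one comparison per outcome over all participants. That reading is an inference; the section does not say so in terms.

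**The concern.** A pre-post change in a knowledge score measures learning only if both tests are taken under the same conditions. In the remote, mailed-materials case they may not be. At baseline the participant has not yet received the slides. At the post-test, given straight after a telephone review of those slides, the participant probably still has them on the table, and the interviewer cannot see. Answers read from the page would then be scored as knowledge gained.

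The study has a single group, so no control arm would carry the same shift and cancel it. The bias, if present, runs toward a larger gain. It concerns the knowledge items only; interest, expectancy and intention items have no answers to look up.

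**Working it through.** **Sequence, mailed remote delivery, as documented**

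| Step | Source | Slides in participant's hands? |
|---|---|---|
| Consent, then pre-test | 4.4B | No, if mailing follows baseline (4.3B) |
| Handouts and brochure mailed | 4.3B | Arriving |
| Educator reviews them by telephone | 4.3B | Yes |
| Post-test on completion of the module, by telephone | 4.4B | Likely yes |

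For emailed, texted or Zoom materials, the order relative to the pre-test is not given, and a Zoom viewer need not hold a copy.

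**The plan's own figure first.** Section 14.3 gives 50 to 100 participants, 80% power, standardized effect 0.3 to 0.4 and two-sided 5%. With n = ((1.960 + 0.842)/d)²:
- d = 0.4: (2.802/0.4)² = 49.1, so 50
- d = 0.3: (2.802/0.3)² = 87.2, so 88

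Paired-t power is 0.792 for N = 50 at d = 0.4, and 0.844 for N = 100 at d = 0.3. The stated range is reproduced and is not in dispute.

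**Illustration on assumed inputs.** The documents give neither the remote share p nor any score inflation b (in SD of the change). Both are assumed here, with no true gain and b averaged over all remote participants:
- overall shift = p × b
- SD of the change = √(1 + p(1 − p)b²)
- chance of p < 0.05 from the noncentral t with N − 1 degrees of freedom and noncentrality √N × shift/SD

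| p | b | Shift (SD) | N = 50 | N = 100 |
|---|---|---|---|---|
| 0.25 | 0.1 | 0.025 | 0.053 | 0.057 |
| 0.50 | 0.1 | 0.050 | 0.064 | 0.078 |
| 0.50 | 0.3 | 0.150 | 0.177 | 0.312 |
| 0.80 | 0.1 | 0.080 | 0.086 | 0.124 |
| 0.80 | 0.3 | 0.240 | 0.379 | 0.655 |

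The nominal value is 0.05. The results run from negligible to serious, and nothing in the documents says which row applies.

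**Precision of the proposed check.** The 95% CI half-width for a mean change is t(0.975, n − 1)/√n: 0.47 SD with 20 people, 0.28 SD with 50 and 0.22 SD with 80. A breakdown by whether materials were put away can describe but not settle the matter.

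**The case against.** The strongest objection is that no fault is documented. The survey (Appendix C) and any remote script are not in the text available for review, and either may already tell participants to set the materials aside. That stands: the absence of an instruction from the available text is not evidence that none exists, and the fix has to be conditional. The fidelity checklist in section 17.0 does not decide it, since it is described as covering how the slides are reviewed, not the conditions of the post-test.

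The order of events is also documented only for mailed materials, in a parenthesis describing a timing variable that may itself vary. Anyone holding the materials at both tests, or at neither, does not show the asymmetry. In-person attendees take home a brochure that, according to section 4.0, reinforces the slide content, so access to materials is not peculiar to remote delivery. Both points narrow the concern; neither removes it for mailed delivery.

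A reader might go further and infer that section 14.2 is deficient unless it breaks results down by delivery mode and by high-risk tract. The documents do not support that as a required change. Section 4.3B already states "For analysis purposes, intervention delivery method (pre-COVID in-person/telephone/online) will be tracked", and section 4.4B geocodes addresses for a neighborhood analysis. Use is intended; only the method is unwritten, and that is missing detail. Such breakdowns would be imprecise: under assumed splits from 20/80 to 50/50, power for a 0.3 SD difference between two groups is 22% to 32% at N = 100 and 13% to 18% at N = 50. Mode is also only a rough stand-in for having the materials at hand.

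**Conclusion.** The concern holds in a limited form. For participants whose materials are mailed after baseline, the procedures as written allow the knowledge post-test to be open-book when the pre-test was not. In a single-group design this could overstate a primary outcome. It rests on two assumptions that the documents leave open: that no script already deals with it, and that some participants consult what they hold.

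The table might be read as an estimate of the bias, or as showing that a positive knowledge result would be false. It shows neither. The shifts of 0.025 to 0.24 SD come wholly from assumed inputs and a zero true gain, and no size is claimed. The sample size, the choice of tests and the other primary outcomes are not called into question. The case for acting is that the remedy is cheap and removes a doubt that cannot be resolved after the data are in.

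**What to change.** Unless the script already does so, add to section 4.4B, for every delivery mode: *Before the knowledge questions of the post-test, participants are asked to put away all study materials, on paper or on screen. Whether this was done is recorded in REDCap, with the date on which the instruction came into use.*

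Keep the pre-post tests in section 14.2 as primary and add: *For the knowledge score only, mean change with 95% CI will be reported by whether materials were put away (yes / no / surveyed before the instruction), as a descriptive sensitivity check. Possible use of materials at the post-test will be stated as a limitation for participants surveyed before the instruction.* Confining this to knowledge also avoids asking for a pre-post change on items that may be asked only after the session.

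The cost is one script line, one participant-level field, one recorded date and two sentences of analysis text; no extra participants are needed. There are three drawbacks. The field is self-reported. It cannot be completed for people already surveyed. Test conditions change part-way through, so the group surveyed before the instruction also differs in calendar period, and contrasts between the groups should not be read as the effect of the materials.

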## 4.4 Study Procedures

**A. Recruitment and Informed Consent.** The Office of Community Outreach (OCO) has a history of working with multiple community organizations, offering free bilingual education via our community speakers bureau. During our education sessions, community partners coordinate logistics, promote our programs and invite community members to participate. Recruitment of study participants will occur working through these long-standing community partners. Partner sites will promote the study and invite participants to a session to learn more. A recruitment flyer may be used at some sites to advertise the study.

Recruitment efforts will be concentrated in census tracts with the greatest need for intervention, i.e., census tracts identified as high-risk due to socioeconomic factors linked to liver cancer (e.g., % non-Hispanic Black, household stability) and high rates of liver cancer. If no current partners are located in these high-risk census tracts, potential new partners will be identified by searching for community centers, federally qualified health centers, etc.

Individuals who attend the session will be informed about the scope of the study and invited to formally participate by the study team. Individuals interested in participating will be consented by health educator [name], project manager [name], or Co-PI [name] prior to completing the pre-intervention survey. Persons not interested will be thanked for their time and excused. We anticipate recruiting between 50-100 participants, depending on the number of participating community partners and the number of education session completed. Education sessions may be conducted on a one-on-one basis or in a group, depending on the number of interested individuals present at any given session. Individuals who refuse to participate or who withdraw from the project will be treated without prejudice.

Due to the COVID-19 pandemic, in-person recruitment efforts conducted by OCO has ceased. During pandemic-related closures, all study-related activities will be conducted over the phone, online, and through US mail. Recruitment will be conducted over the telephone, and informed consent will be obtained verbally (also over the telephone). Once informed consent is obtained, an oral consent document will be sent via US mail to the participant.

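### Group sessions are allowed, but the tests in 14.2 and the sample size in 14.3 treat participants as independent; if a sizeable share was taught in groups and changes correlate within sessions, the 5% type-I error does not hold

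*Combined protocol and SAP*

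**What the plan says.** Section 4.4 A allows both formats: "Education sessions may be conducted on a one-on-one basis or in a group". Partner sites invite people to a session, and 4.3 B describes interactive teaching with a question period, so people in one group share an educator and a discussion.

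Section 14.2 gives the whole inferential plan for the survey data: mean differences, standard deviations, an effect size, and then "We will compare the pre-post differences using t-tests or Wilcoxon tests, as appropriate". Section 14.3 sizes the study at 50 to 100 for 80% power at a standardised change of 0.3-0.4, two-sided 5%. Neither section mentions an ICC, a design effect, a mixed model or robust standard errors. The cluster wording elsewhere in Section 14 concerns the geospatial analysis.

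Some text limits the reach of the point. Section 4.4 A says "During pandemic-related closures, all study-related activities will be conducted over the phone, online, and through US mail", and 4.3 B adds "By default, the intervention will be conducted over the telephone", with the educator calling the participant. Section 4.3 B also says that "intervention delivery method (pre-COVID in-person/telephone/online) will be tracked", together with timing, for analysis; session membership is not mentioned there.

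On outcomes, 4.4 B places knowledge and self-efficacy in both surveys, then says "The post survey will include similar knowledge questions as well as additional questions specifically related to neighborhood health". Outcome expectancies and intentions are listed only under the post-survey.

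**The concern.** A one-sample t-test or signed-rank test on change scores takes each participant as a separate piece of information. If a session goes well or badly for the whole group, its members' changes move together and the group carries less information than its head count suggests. The mean change stays unbiased as long as session size is unrelated to change, but its standard error is understated. The p-value is then too small and the interval too narrow.

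At stake is the efficacy claim for the education session: whether a significant change in knowledge was really tested at 5%. Power is affected too. The planned t-test appears to keep most of its power partly because it exceeds 5% error; a test that holds 5% has less.

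**Working it through.** **Step 1. Reproduce 14.3.** Inputs from 14.3: two-sided 5%, power 80%, d = 0.3 to 0.4 in units of the SD of the changes. For independent participants, n = ((1.96 + 0.8416)/d)².
- d = 0.4: 7.849/0.16 = 49.1, so 50; with the t distribution, 52.
- d = 0.3: 7.849/0.09 = 87.2, so 88; with the t distribution, 90.

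Power of the paired t-test is 79.2% at n=50, d=0.4 and 84.4% at n=100, d=0.3. The stated range is therefore the independent-participant size, with 100 a rounded-up ceiling. No clustering allowance is stated.

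**Step 2. Assumptions.** The documents do not give group size, ICC of the change scores, or the share taught in groups. I take n=100, groups of 10 (and 5), ICC 0.02, 0.05 and 0.10, and vary the share. One-on-one participants count as sessions of size 1.

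**Step 3. Type-I error of the planned t-test.** DE = 1 + ICC × (Σm²/n − 1), where m is session size; error = 2 × (1 − Φ(1.96/√DE)).

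Example with 30% grouped: three groups of 10 and 70 singles give Σm² = 300 + 70 = 370, so 370/100 − 1 = 2.7. At ICC 0.10, DE = 1.27, 1.96/√1.27 = 1.739, and the error is 8.2%.

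| Share in groups of 10 | Σm²/n − 1 | ICC 0.02 | ICC 0.05 | ICC 0.10 |
|---|---|---|---|---|
| none | 0 | 5.0% | 5.0% | 5.0% |
| 10% | 0.9 | 5.2% | 5.5% | 6.0% |
| 30% | 2.7 | 5.6% | 6.6% | 8.2% |
| half | 4.5 | 6.0% | 7.7% | 10.4% |
| all (upper bound) | 9.0 | 7.1% | 10.4% | 15.5% |

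With groups of 5 and 30% grouped, the error is 5.3-6.4%. At ICC 0.01 with 30% in groups of 10, DE = 1.027 and the error is about 5.3%. Simulation with normal change scores and a random session effect agrees to within a few tenths of a point (30% grouped: 5.4-8.3% across runs). The Wilcoxon test behaves the same way: 5.6-8.2% with 30% grouped and 6.2-10.0% with half.

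**Step 4. What a valid test does.** Session-clustered standard errors with the CR2 correction and Satterthwaite degrees of freedom gave simulated type-I error of 4.7-5.7% in the n=100 scenarios. Power at n=100, d=0.3:

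| Share in groups of 10 | Planned t-test, ICC 0.02-0.10 | CR2, ICC 0.02-0.10 | CR2, ICC 0 |
|---|---|---|---|
| 30% (df 26.1) | 84-82% | 80-74% | 82% |
| half (df 17.2) | 83-80% | 77-66% | 81% |

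With nobody in groups, CR2 has 99 degrees of freedom and equals the t-test.

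**The case against.** The strongest reply is that the point may hardly bite. The current text is Amendment 8: in-person recruitment has stopped and the default is a telephone call to one person. Group size, ICC and share are all assumed, and with 10% or fewer grouped the error stays close to 5% (at most about 6.1% in simulation). This stands, and it is why the conclusion is conditional. It does not remove the point, because 4.4 still permits groups and 4.3 B keeps pre-COVID in-person delivery as an analysis category.

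A second reply is that the clustered test can be costly. At the permitted n=50 with everyone in five groups of 10, power at d=0.4 falls from 79% under independence to 57% with the clustered test even at ICC 0. For a study that calls itself a pilot, an unconditional switch of primary test is debatable. This also stands, and the fix below is conditional for that reason.

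A reader might infer that session membership is not captured at all. The text does not support that: Section 5.0 leaves the data dictionary to the team, the survey and sign-in sheet are appendices whose content is not in the text reviewed, and Section 17.0 provides a fidelity checklist. One can say only that no session identifier is described.

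Nor do the documents show that past sessions can mostly be rebuilt. Under Section 10.0 "research staff will date and sign the informed consent document", and the form is "uploaded into the study REDCap database". A date plus in-person delivery cannot separate two sessions on one day, or one-on-one from group teaching, and sign-in sheets are destroyed after geocoding.

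**Conclusion.** The point holds as a conditional one. The plan permits group teaching and describes no analysis that allows for it. With a sizeable grouped share and positive within-session correlation, the stated 5% is exceeded: roughly 5.6-8.2% with 30% grouped and 6.0-10.4% with half, under assumed groups of 10, ICC 0.02-0.10 and n=100. It is minor if most delivery was by individual telephone call, and nil from this source if all was one-on-one.

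A reader might take the 15.5% in the all-grouped row as the likely size. The documents do not support this: that row fits poorly with the telephone default and is only an upper bound. Nor does the point imply that the estimated mean change is biased.

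The scope is outcomes described as asked both before and after, namely knowledge and self-efficacy. Of these, only knowledge is a named primary outcome. This is a correctable gap in inference.

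**What to change.** 1. Record a session ID in REDCap, with each one-on-one participant as their own session. Rebuild past in-person sessions as far as records allow, from delivery method, consent dates, the fidelity checklist if dated, and any remaining sign-in sheets, and state that this may be incomplete. Do not split a date by signing staff alone, because 4.4 A lists three roles who may take consent. In simulation, wrongly halving each group of 10 leaves the clustered test at 5.1-6.7% error with 30% grouped.
2. In 14.2, for knowledge and self-efficacy, report the mean change with session-clustered standard errors and a small-sample correction (for example CR2 with Satterthwaite degrees of freedom) next to the planned test. Where a material share was taught in groups, rest the 5% claim on the clustered result, and note low power if sessions are few. Fix in advance what counts as material.
3. Report the number and size of group sessions.
4. State in 14.3 that the 80% power assumes independent participants.

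Cost: one data field, some SAP wording, reconstruction work, and wider intervals where sessions were grouped (median width up 3-11% with 30% in groups of 10, n=100, ICC 0.02-0.10). Power falls even without correlation: at n=100, d=0.3, from about 84% to 82% with 30% in groups of 10. The method does not cover correlation across sessions at one site or under one educator.
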